## 5.5 BIOBANKING

Not applicable.

## 5.6 OTHER ASSESSMENTS

Not applicable.

## 5.7 APPROPRIATENESS OF MEASUREMENTS

All measurements performed during this trial are standard measurements and will be performed in order to monitor subjects' safety and to determine pharmacokinetic parameters in an appropriate way. The scheduled measurements will allow monitoring of changes in vital signs, standard laboratory values, ECG parameters, and local tolerability that might occur as a result of administration of trial medication. The safety assessments are standard, are accepted for evaluation of safety and tolerability of IV and SC administered drug, and are widely used in clinical trials. The pharmacokinetic parameters and measurements outlined in Section [5.4](#) are generally used assessments of drug exposure.

## 6. INVESTIGATIONAL PLAN

### 6.1 VISIT SCHEDULE

Exact times of measurements outside the permitted time windows will be documented. The acceptable time windows for screening and the end of trial examination are provided in the [Flow Chart](#).

Study measurements and assessments scheduled to occur 'before' trial medication administration on Day 1 are to be performed and completed within a 3 h-period prior to the trial drug administration (including blank values for PK).

The acceptable deviation from the scheduled time for vital signs, ECG, and laboratory tests will be:

- $\pm 30$  min up to and including 48 h
- $\pm 120$  min from 48 h up to Day 8
- $\pm 4$ h from Day 8 onwards up to the last measurements

The tolerance for blood sampling for PK, [REDACTED] will be:

- $\pm 1$  min up to and including 30 min
- $\pm 5$  min from 30 min up to and including 12 h
- $\pm 15$  min from 12 h up to and including 48 h
- $\pm 60$  min from 48 h up to Day 8
- $\pm 4$ h from Day 8 onwards up to the last measurements

If scheduled in the [Flow Chart](#) at the same time as a meal, blood sampling, vital signs, and 12-lead ECG recordings have to be done first. Furthermore, if several measurements including venepuncture are scheduled for the same time, venepuncture should be the last of the measurements due to its inconvenience to the subject and possible influence on physiological parameters.

For planned blood sampling times, refer to the [Flow Chart](#). While these nominal times should be adhered to as closely as possible, the actual sampling times will be recorded and used for the determination of pharmacokinetic parameters.

If a subject misses an appointment, it will be rescheduled if possible. The relevance of measurements outside the permitted time windows will be assessed no later than at the Report Planning Meeting.

### 6.2 DETAILS OF TRIAL PROCEDURES AT SELECTED VISITS

#### 6.2.1 Screening period

After having been informed about the trial, all subjects will provide written informed consent in accordance with GCP and local legislation prior to enrolment in the study.

Proprietary confidential information © 2021 Boehringer Ingelheim International GmbH or one or more of its affiliated companies

For information regarding laboratory tests (including drug and virus screening), ECG, vital signs, and physical examination, refer to Sections [5.2.3](#) to [5.2.5](#).

### **6.2.2 Treatment period**

Each subject will receive one dose of trial medication (BI 765080) at Visit 2.

Trial medication will be administered as IV infusion or SC injection by the investigating physician or [redacted] designee. Details on treatments and procedures of administration are described in Section [4.1.4](#).

Study participants will be admitted to the trial site on Day -1 and kept under close medical surveillance for at least 48 h (IV group) or 72 h (SC group) following drug administration. The subjects will then be allowed to leave the trial site after formal assessment and confirmation of their fitness by the investigator or [redacted] designee. On all other study days, subjects will be treated in an ambulatory fashion.

For details on time points and procedures for collection of blood samples for PK analysis, refer to [Flow Chart](#) and Section [5.3.2](#).

The safety measurements performed during the treatment period are specified in Section [5.3](#) of this protocol and in the [Flow Chart](#). For details on times of all other trial procedures, refer to the [Flow Chart](#). AEs and concomitant therapy will be assessed continuously from screening until the end of trial examination.

### **6.2.3 Follow-up period and trial completion**

For AE assessment, laboratory tests, recording of ECG and vital signs, and physical examination during the follow-up period, see Sections [5.2.2](#) to [5.2.5](#).

Subjects who discontinue treatment before the end of the planned treatment period should undergo the EoTrial Visit.

If needed in the opinion of the investigator, additional visits may be scheduled after the EoTrial Visit for continued safety monitoring.

All abnormal values (including laboratory parameters) that are assessed as clinically relevant by the investigator will be monitored using the appropriate tests until a return to a medically acceptable level is achieved. (S)AEs persisting after a subject's EoTrial Visit must be followed until they have resolved, have been sufficiently characterised, or no further information can be obtained.

## 7. STATISTICAL METHODS AND DETERMINATION OF SAMPLE SIZE

### 7.1 STATISTICAL DESIGN – MODEL

The main objective of this trial is to investigate the absolute bioavailability of (SC) injection of 100 mg BI 765080 (Test, T) compared with IV dose of 100 mg BI 765080 (Reference, R) following administration on the basis of the primary and secondary safety and pharmacokinetic endpoints, as listed in Section [2.1.2](#) and [2.1.3](#). The trial is designed to allow inter-subject comparisons and will be evaluated statistically by use of a linear model for logarithmically transformed PK endpoints and descriptive analysis for AEs.

The assessment of safety and tolerability as well as local tolerability is a further objective of this trial, and will be evaluated by descriptive statistics for the parameters specified in Section [2.2.2.2](#) and [2.2.2.3](#).

### 7.2 NULL AND ALTERNATIVE HYPOTHESES

The absolute bioavailability of SC injection compared with IV dose will be estimated by the ratios of the geometric means (test/reference), and their corresponding 2-sided 90% confidence intervals (CIs) will be provided. This method corresponds to the two one-sided t-test procedure, each at the 5% significance level. Since the main focus is on estimation and not testing, a formal hypothesis test and associated acceptance range is not specified.

### 7.3 PLANNED ANALYSES

#### Analysis sets

Statistical analyses will be based on the following analysis sets:

- Treated set (TS): The treated set includes all subjects who were allocated and treated with at least one dose of study drug. The treated set will be used for safety analyses.
- Pharmacokinetic parameter analysis set (PKS): This set includes all subjects in the treated set (TS) who provide at least one PK endpoint that was defined as primary or secondary and was not excluded due to a protocol violation relevant to the evaluation of PK or due to PK non-evaluability (as specified in the following subsection ‘Pharmacokinetics’). Thus, a subject will be included in the PKS, even if he/she contributes only one PK parameter value to the statistical assessment. Descriptive and model based analyses of PK parameters will be based on the PKS.

Adherence to the protocol will be assessed by the trial team. Important protocol violation (IPV) categories will be specified in the IPD specification file prior to trial initiation, IPVs will be identified no later than in the Report Planning Meeting, and the IPV categories will be updated as needed.

### Pharmacokinetics

The pharmacokinetic parameters listed in Section [2.1](#) for drug BI 765080 will be calculated according to the relevant SOP of the Sponsor (current version).

Plasma concentration data and parameters of a subject will be included in the statistical pharmacokinetic (PK) analyses if they are not flagged for exclusion due to a protocol violation relevant to the evaluation of PK (to be decided no later than in the Report Planning Meeting) or due to PK non-evaluability (as revealed during data analysis, based on the criteria specified below). Exclusion of a subject's data will be documented in the CTR.

Relevant protocol violations may be

- Incorrect trial medication taken, i.e. the subject received at least one dose of trial medication the subject was not assigned to
- Incorrect dose of trial medication taken
- Use of restricted medications

Plasma concentrations and/or parameters of a subject will be considered as non-evaluable, if for example

- A predose concentration is  $>5\% C_{max}$  value of that subject
- Missing samples/concentration data at important phases of PK disposition curve.

Plasma concentration data and parameters of a subject which is flagged for exclusion will be reported with its individual values but will not be included in the statistical analyses.

Descriptive and inferential statistics of PK parameters will be based on the PKS.

Only concentration values within the validated concentration range and actual sampling times will be used for the calculation of pharmacokinetic parameters. Concentrations used in the pharmacokinetic calculations will be in the same format provided in the bioanalytical report, (that is, to the same number of decimal places provided in the bioanalytical report).

#### **7.3.1 Primary endpoint analyses**

##### Primary analyses

The statistical model used for the analysis of the primary endpoints will be an analysis of variance (ANOVA) model on the logarithmic scale. That is, the PK endpoints will be log-transformed (natural logarithm) prior to fitting the ANOVA model. This model will include effects accounting for the following source of variation: treatment and matching pair. The effect of treatment will be considered as fixed. For each matched pair in the study a pair number will be assigned for analysis purpose. The resulting variable 'matched pair' will be considered as random effect. The model is described by the following equation:

$$y_{km} = \mu + \tau_k + s_m + e_{km}, \text{ where}$$

$y_{km}$  = logarithm of response measured on subject m receiving treatment k,

Proprietary confidential information © 2021 Boehringer Ingelheim International GmbH or one or more of its affiliated companies

$\mu$  = the overall mean,

$\tau_k$  = the  $k^{\text{th}}$  treatment effect,  $k = 1, 2,$

$s_m$  = the effect associated with the  $m^{\text{th}}$  matching pair,  $m = 1, 2, \dots, 14,$

$e_{km}$  = the random error associated with the  $m^{\text{th}}$  subject who received treatment  $k.$

where  $s_m \sim N(0, \sigma_B^2)$  i.i.d.,  $e_{km} \sim N(0, \sigma_W^2)$  i.i.d.,  $\sigma_W^2$  and  $s_m, e_{km}$  are independent random variables.

Point estimates for the ratios of the geometric means (test/reference) for the primary endpoints (see Section 2.1) and their two-sided 90% confidence intervals (CIs) will be provided.

For each endpoint, the difference between the expected means for  $\log(T)-\log(R)$  will be estimated by the difference in the corresponding adjusted means (Least Squares Means). Additionally their two-sided 90% confidence intervals will be calculated based on the residual error from the ANOVA and quantiles from the t-distribution. These quantities will then be back-transformed to the original scale to provide the point estimate and 90% CIs for each endpoint.

In addition to the model based approach all parameters will be calculated and analysed descriptively.

[figure not shown]
### **7.3.2 Secondary endpoint analyses**

The secondary PK endpoints (refer to Section 2.1.3) will be calculated according to the BI SOP ‘Standards and processes for analyses performed within Clinical Pharmacokinetics/ Pharmacodynamics’ and will be assessed statistically using the same methods as described for the primary endpoints.

Drug-related adverse event will be presented descriptively by treatment group.

#### **7.3.3.2 Safety and tolerability analyses**

Further safety and tolerability endpoints will be analysed descriptively.

#### 7.3.4 Safety analyses

Safety will be analysed based on the assessments described in Section [2.2.2.2](#) and [2.2.2.3](#). All treated subjects (TS, refer to Section [7.2](#)) will be included in the safety analysis. Safety analyses will be descriptive in nature and based on BI standards. No hypothesis testing is planned.

For all analyses, the treatment actually administered (= treatment at onset) to the subject will be used (any deviations from the treatment will be discussed in the minutes of the Report Planning Meeting).

Treatments will be compared in a descriptive way. Tabulations of frequencies/proportions will be used to evaluate categorical (qualitative) data, and tabulations of descriptive statistics will be used to analyse continuous (quantitative) data.

Measurements (such as ECG, vital signs, or laboratory parameters) or AEs will be assigned to treatments (see Section [4.1](#)) based on the actual treatment at the planned time of the measurement or on the recorded time of AE onset (concept of treatment emergent AEs). Therefore, measurements planned or AEs recorded prior to first intake of trial medication will be assigned to the screening period, those between first trial medication intake and end of trial examination (including the anticipated REP (see Section [1.2.3](#))) will be assigned to the treatment period. These assignments including the corresponding time intervals will be defined in detail in the TSAP. Note that AEs occurring after the last per protocol contact but entered before final database lock will be reported to Pharmacovigilance only and will not be captured in the trial database.

Adverse events will be coded using the Medical Dictionary for Regulatory Activities (MedDRA). Frequency, severity, and causal relationship of AEs will be tabulated by treatment, system organ class, and preferred term. SAEs, AESIs (see Section [5.2.6.1](#)), and other significant AEs (according to ICH E3) will be listed separately.

Previous and concomitant therapies will be presented per treatment group without consideration of time intervals and treatment periods.

Laboratory data will be compared to their reference ranges. Values outside the reference range as well as values defined as possibly clinically significant will be highlighted in the listings. Additionally, differences from baseline will be evaluated.

Vital signs or other safety-relevant data will be assessed with regard to possible on-treatment changes from baseline.

Relevant ECG findings will be reported as AEs.

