## FLOW CHART - IV GROUP

Period	Visit	Day	Planned time (relative to first drug administration) [h:min]	Approximate clock time of actual day [h:min]	Event and comment	Safety laboratory	PK serum	12-lead ECG	Vital signs (BP, PR)	Questioning for AEs and concomitant therapy 	Query regarding local tolerability 
SCR	1	-21 to -3			Screening (SCR) 	x		x	x		
	2	-2	-48:00	8:00	Ambulatory visit	x 				x	
		-1	-14:00	18:00	Admission to trial site	x 				x	
		1	-3:00	06:00	Allocation to treatment 	x 	x 	x 	x 	x 	
			0:00	08:00	Drug administration start of infusion						
			0:30	08:30	end of infusion		x	x		x	x
			2:00	10:00	Light breakfast 		x	x	x		x
			4:00	12:00			x	x	x	x	
			8:00	16:00	Snack (voluntary) 		x	x	x		
			12:00	20:00			x	x	x	x	x
			24:00	08:00	Breakfast 	x	x	x	x	x	
			34:00	18:00	Dinner 		x		x	x	
			48:00	08:00	Breakfast  , discharge from trial site (confirmation of fitness) 		x	x	x	x	
		4	72:00	08:00	Ambulatory visit		x				x
		6	120:00	08:00	Ambulatory visit		x				x
		8	168:00	08:00	Ambulatory visit	x	x	x	x	x	
		11	240:00	08:00	Ambulatory visit		x				x
		14	312:00	08:00	Ambulatory visit	x	x	x	x	x	
		21	480:00	08:00	Ambulatory visit		x	x	x	x	
		28	648:00	08:00	Ambulatory visit	x	x	x	x	x	
		56	1320:00	08:00	Ambulatory visit	x	x	x	x	x	
FU	3	56 to 59			End of trial (EoTrial) examination 	x		x	x	x	x

1. Subject must be informed and written informed consent obtained prior to starting any screening procedures. Screening procedures include physical examination, check of vital signs, inclusive body temperature if it is still needed based on the status of pandemic, ECG, safety laboratory (including drug screening), demographics (including determination of body height and weight, smoking status and alcohol history), relevant medical history, concomitant therapy and review of inclusion/exclusion criteria.
2. The time is approximate; the procedure is to be performed and completed within the 3 h prior to drug administration.
3. If several actions are indicated at the same time, the intake of meals will be the last action.
4. At the end of trial visit the EoTrial examination includes physical examination, vital signs, ECG, safety laboratory, recording of AEs and concomitant therapies. EOT to be performed not before last PK sampling.

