## FLOW CHART - SC GROUP

Period	Visit	Day	Planned time (relative to first drug administration) [h:min]	Approximate clock time of actual day [h:min]	Event and comment	Safety laboratory	PK serum	12-lead ECG	Vital signs (BP, PR)	Questioning for AEs and concomitant therapy 	Query regarding local tolerability 
SCR	1	-21 to -3			Screening (SCR) 	x		x	x		
	2	-2	-48:00	8:00	Ambulatory visit	x 			x	x	
		-1	-14:00	18:00	Admission to trial site	x 				x	
		1	-3:00	06:00	Allocation to treatment 	x 	x 	x 	x 	x 	
			0:00	08:00	Drug administration/injection						x
			0:30	08:30						x	x
			1:00	09:00					x	x	
			1:30	09:30					x	x	
			2:00	10:00	Light breakfast 			x	x	x	
			3:00	11:00				x	x	x	
			4:00	12:00			x	x	x	x	x
			8:00	16:00	Snack (voluntary) 			x	x	x	
			12:00	20:00			x	x	x	x	x
		2	24:00	08:00	Breakfast 	x	x	x	x	x	x
			3	48:00	08:00		x	x	x	x	x
		4	72:00	08:00	Breakfast  , discharge from trial site (confirmation of fitness  )	x		x	x	x	x
			5	96:00	08:00	Ambulatory visit		x		x	x
			6	120:00	08:00	Ambulatory visit		x		x	x
			7	144:00	08:00	Ambulatory visit	x	x	x	x	x
			8	168:00	08:00	Ambulatory visit		x		x	
			11	240:00	08:00	Ambulatory visit		x		x	
			14	312:00	08:00	Ambulatory visit	x	x	x	x	
			21	480:00	08:00	Ambulatory visit		x	x	x	
			28	648:00	08:00	Ambulatory visit	x	x	x	x	
			56	1320:00	08:00	Ambulatory visit	x	x	x	x	
FU	3	56 to 59			End of trial (EoTrial) examination 	x		x	x	x	

1. Subject must be informed and written informed consent obtained prior to starting any screening procedures. Screening procedures include physical examination, check of vital signs, inclusive body temperature if it is still needed based on the status of pandemic, ECG, safety laboratory (including drug screening), demographics (including determination of body height and weight, smoking status and alcohol history), relevant medical history, concomitant therapy and review of inclusion/exclusion criteria.
2. The time is approximate; the procedure is to be performed and completed within the 3 h prior to drug administration.
3. If several actions are indicated at the same time, the intake of meals will be the last action.

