4. At the end of trial visit the EoTrial examination includes physical examination, vital signs, ECG, safety laboratory, recording of AEs and concomitant therapies. EOT to be performed not before last PK sampling.
5. Only urine drug screening and alcohol breath test will be done at this time
6. AEs and concomitant therapies will be recorded throughout the trial, but will be specifically asked for at the times indicated in the [Flow Chart](#) above.
7. Confirmation of fitness includes physical examination.
8. Standardized assessment of local tolerability using the criteria swelling, induration, heat, redness, pain or other findings.
9. SARS-CoV-2 PCR test will be performed prior to admission on Day -1 or Day -2 if it is needed in the current status of pandemic.
11. Safety laboratory to be taken and to be medically evaluated within 3 days prior to administration of study drug; this safety laboratory assessment can be omitted if the screening examination is performed on Days -5 to Day -3.

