#### **3.2 DISCUSSION OF TRIAL DESIGN, INCLUDING THE CHOICE OF CONTROL GROUP**

This study will explore the absolute bioavailability, safety, tolerability and pharmacodynamics following intravenous (IV) infusion or subcutaneous (SC) injection of BI 765080 in matched pairs of healthy male subjects (matching is done based on age and body weight, see Section [3.3](#)). By dosing test and reference treatment to a matched pair on the same day the influence of confounding factors can be reduced to a minimum.

The trial will be conducted open-label. Blinding is not possible because the treatments are distinguishable. The open-label treatment is not expected to bias results, since the study endpoints are derived from measurement of plasma concentrations of the analyte, which are provided by a bioanalytical laboratory that is blinded to treatment allocation.

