7.8.5 Local tolerability

Local tolerability (absence or presence of "swelling", "induration", "heat", "redness", "pain", or "other findings") will be summarized with counts and percentages overall (i.e. over all on-treatment time points, cf. [Section 6.1](#)) as well as by time point.

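### The SC and IV flow charts schedule AE questioning and local-tolerability checks at different times, so the descriptive comparison of routes is not fully like for like

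*Protocol*

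**What the plan says.** - **Comparison.** Protocol 7.3.4: "Treatments will be compared in a descriptive way", and "No hypothesis testing is planned". Protocol 7.3.2 presents drug-related AEs by treatment group; Section 2.1.3 lists them as a secondary endpoint. Section 7.1 makes safety and local tolerability a further objective.
- **AE questioning.** Each flow chart carries the same footnote 6: "AEs and concomitant therapies will be recorded throughout the trial, but will be specifically asked for at the times indicated in the" chart. Section 5.2.6.2.1 treats those times as a minimum. Each arm has its own chart, so the minimum differs by arm. Time zero is "Drug administration start of infusion" in one chart and "Drug administration/injection" in the other.
- **In-house stay.** Section 6.2.2: subjects are "kept under close medical surveillance for at least 48 h (IV group) or 72 h (SC group) following drug administration".
- **Local tolerability.** Section 5.2.5.1 makes this an investigator assessment. SAP 7.8.5 says the findings "will be summarized with counts and percentages overall (i.e. over all on-treatment time points", and also by time point. SAP Section 7 bases percentages on all subjects in the set, whether or not a value is missing.
- **Open label.** Protocol 3.2: "The open-label treatment is not expected to bias results, since the study endpoints are derived from measurement of plasma concentrations".

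Neither document mentions the unequal schedules or restricts any comparison to shared times.

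**The concern.** Asking a subject how he feels, or inspecting a site, raises the chance that a mild, short-lived event is written down. If one arm is asked more often, it can show more such events although the two routes are equally well tolerated. The SC chart has post-dose rows at 1:00, 1:30 and 3:00 that the IV chart lacks altogether. The difference in schedule therefore does not depend on how individual marks are read.

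The reassurance in Section 3.2 rests on endpoints derived from concentrations. It does not reach drug-related AEs or local tolerability, which staff who know the route elicit and judge. What is at stake is the fairness of the side-by-side safety tables. The PK results are not affected.

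**Working it through.** The documents give no figure to reproduce here, so the check is a count of scheduled looks followed by two illustrations.

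**Step 1. Marks in the two flow charts (post-dose).** Some cell positions are uncertain in the text copy of the charts. In the IV chart, lone marks at 2:00, 72:00, 120:00 and 240:00 fall under local tolerability but might belong to AE questioning; that is the alternative reading below. Several later SC rows (48:00, and 96:00 onward) are visibly offset. Counts beyond the first day are therefore less secure than those for the first 12 h.

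| Looks | SC | IV | IV, alternative |
|---|---|---|---|
| AE prompts, to 12 h | 8 | 3 | 4 |
| AE prompts, to 48 h | 10 | 6 | 7 |
| AE prompts, whole trial | 21 | 12 | 16 |
| Local checks, to 12 h | 4 | 3 | 2 |
| Local checks, to 48 h | 6 | 3 | 2 |
| Local checks, whole trial | 10 | 7 | 3 |

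- AE prompts to 12 h: SC at 0:30, 1:00, 1:30, 2:00, 3:00, 4:00, 8:00 and 12:00; IV at 0:30, 4:00 and 12:00 (plus 2:00 on the alternative).
- Local checks: SC at 0, 0:30, 4, 12, 24, 48, 72, 96, 120 and 144 h; IV at 0:30, 2, 12, 72, 120 and 240 h and end of trial (only 0:30, 12 h and end of trial on the alternative).
- Shared local checks: 0:30, 12, 72 and 120 h (4), or 0:30 and 12 h (2).
- IV looks that SC lacks: an AE question at 34 h and, as extracted, local checks at 2 h, 240 h and end of trial.

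**Step 2. Overlap of a short symptom with an AE prompt.** Assume onset uniform on [0, W] and duration d. The overlap is the share of onsets x for which some prompt t satisfies x ≤ t ≤ x + d.

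- W = 4 h, d = 1 h. SC: the qualifying onsets fill the window, 4/4 = 100%. IV: (0.5 + 1)/4 = 37.5%; alternative (0.5 + 1 + 1)/4 = 62.5%.
- W = 12 h, d = 1 h. SC: (4 + 1 + 1)/12 = 50%. IV: (0.5 + 1 + 1)/12 = 21%; alternative 3.5/12 = 29%.
- W = 12 h, d = 2 h. SC: (4 + 2 + 2)/12 = 67%. IV: (0.5 + 2 + 2)/12 = 37.5%; alternative (2 + 2 + 2)/12 = 50%.

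These figures describe the prompts alone. They are not rates of AE capture, because spontaneous reports and recall at a later prompt are left out.

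**Step 3. Overall local-tolerability percentage.** Read it as the share of subjects with a finding at any on-treatment look. With k looks and an assumed per-look probability p, equal in both arms and independent between looks, P(any) = 1 − (1 − p)^k.

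| p (assumed) | SC, k = 10 | IV, k = 7 | IV alternative, k = 3 |
|---|---|---|---|
| 0.02 | 18% | 13% | 6% |
| 0.05 | 40% | 30% | 14% |
| 0.10 | 65% | 52% | 27% |

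At p = 0.05 this is about 5.6 of 14 SC subjects and 4.2 (or 2.0) of 14 IV subjects, with no true difference. Independence puts this at the upper end: a finding that lasts for days would be seen under either schedule.

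**Step 4. Equal looks.** With the same k in both arms the formula gives the same value, so the part of the difference due to the schedule is zero.

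**The case against.** The case on the other side is substantial.

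- **Capture is not limited to prompts.** Subjects must report AEs spontaneously with onset and end times (5.2.6.2.1), assessment is continuous (6.2.2), and both arms are under close surveillance in-house. A symptom at 2.5 h can be reported at once or recalled at 4:00. SAP 7.8.1 counts subjects with AEs, not events. This stands, and it is why the overlap figures in Step 2 cannot be read as the size of the bias.
- **Direction.** A reader might infer that every difference pushes towards more events in SC. The documents do not support that: the IV chart has looks that SC lacks (Step 1), and to 12 h the local checks are 4 against 3. Only the net count favours SC.
- **Stakes.** A reader might infer that an SC-versus-IV tolerability contrast is the planned basis for moving to SC. Section 1.3 says only that local tolerability is examined after SC injection. Safety is descriptive, with 14 subjects per arm. Closer observation of a route not used in the first-in-human trial may be deliberate, although the documents do not say so.
- **Partly handled.** SAP 7.8.5 also tabulates by time point, so shared times can be compared by eye.
- **Limits of shared times.** Using shared times alone would drop 6 of 10 SC local checks (60%), or 8 of 10 (80%) on the alternative reading. Nor is 0:30 the same moment in both arms: it is the end of the infusion for IV and roughly half an hour after a 60-second injection for SC. A shared-time percentage should therefore be added and should not replace the planned one.

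None of this makes the schedules equal, and no reading of the marks removes the rows found only in the SC chart.

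**Conclusion.** The point holds as a modest, cheaply corrected weakness. The scheduled looks differ by route: 8 AE prompts against 3 or 4 in the first 12 h, and 10 local checks against 7 or 3 over the trial as extracted. The planned by-route summaries do not allow for this. The net tilt is towards more recorded mild, transient events in SC.

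For AEs the size cannot be estimated from the documents, and it may be small. For the overall local-tolerability percentage the link to the number of looks is direct. The illustrated gap is 5 to 13 percentage points as extracted (18% − 13% at p = 0.02; 65% − 52% at p = 0.10), and wider on the alternative reading. It rests on assumed per-look probabilities, independent looks and an any-time-point reading of the overall percentage. One subject is 1/14 = 7.1 percentage points, so even a small difference in ascertainment would be visible in these tables.

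It does not follow that SC will show more events than IV, or that the safety tables are unusable. The exact marks should be confirmed against the PDF charts.

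**What to change.** 1. **Flow charts.** Reconcile them so that AE questioning and local-tolerability checks fall at the same post-dose times while both arms are in-house (to 48 h), or state why they differ. The choice of times is for the sponsor. If the IV arm took on every SC prompt in the first 12 h, that would be 8 − 3 = 5 further spoken questions (4 on the alternative reading) for each of 14 subjects who are already on site, with no extra blood or visits.
2. **SAP 7.8.5.** Keep the planned overall and by-time-point tables. Add an overall percentage restricted to time points scheduled in both arms, and use it for the between-route comparison. State any remaining schedule difference as a limitation.
3. **Protocol 3.2.** Confine the statement that open-label treatment should not bias results to the PK endpoints.

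The cost is a little more site documentation for IV subjects, one extra table and two sentences. If the charts are not aligned, or the visits have already taken place, items 2 and 3 can still be done, but the added percentage would then rest on only 4, or possibly 2, shared local checks.
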